#### **7.5.3.1. Investigators’/Surgeons’ Assessment of Patients’ Response to Major Surgery**

The Investigators’/Surgeons’ assessment (using the 4-point surgery response scale detailed in protocol [Appendix D](#)) of the patient’s hemostatic response to rFIXFc at 24 hours post-surgery will be summarized categorically and with descriptive statistics for all major surgeries for the FAS. Categorically, the number and percentage of surgeries given each rating will be tabulated. Percentages will be based on the number of surgeries for which a response was provided. Since the response is given as an ordered ordinal scale, the responses have also been given a numeric score (Excellent=1, Good=2, Fair=3, Poor/none=4). A lower average score indicates a better Investigators’/Surgeons’ assessment of the patients’ response to surgery with rFIXFc. Descriptive statistics will be provided using the numeric value of the 4-point scale.

#### **7.5.3.2. Number of Injections and Dose Required to Maintain Hemostasis During Major Surgery**

The number of injections, the mean dose per injection (IU/kg), and the total dose (IU/kg) required to maintain hemostasis during surgery will be summarized for all major surgeries for patients in the FAS. The number of injections per surgery will be summarized categorically (0, 1, 2, 3, 4, >4) and with descriptive statistics. Percentages for the categorical summary will be based on the number of major surgeries. The mean dose per injection and total dose required to maintain hemostasis will be summarized using descriptive statistics. The mean dose per injection will be determined as the average dose across all injections per surgery (including the loading dose); the total dose will be determined as the sum across all injections (including the loading dose) per surgery.

#### **7.5.3.3. Estimated Total Blood Loss and Transfusions Received during Major Surgery**

The estimated total blood loss during and post each major surgical procedure will be summarized using descriptive statistics. These data will additionally be summarized for the number of transfusions per surgery (regardless of the type of transfusion), the number of transfusions summed across all surgeries for each type of transfusion, and the number of surgeries requiring each type of transfusion will be summarized categorically for all major surgeries for the FAS. Percentages in the categorical summaries will be based on the number of major surgeries for which the respective data is available.

#### **7.5.3.4. Total rFIXFc Consumption per Major Surgery**

Total consumption (IU/kg) per major surgery on the day of surgery, for the first 2 weeks following surgery (Days 1-3, 4-14, and 1-14), and for the overall surgical/rehabilitation period will be summarized using descriptive statistics for all major surgeries for the FAS. The day of surgery refers to the calendar day of the surgery and includes the loading dose given for that surgery. The first 2 weeks following surgery begins the day after surgery and extends for 14 calendar days. The overall surgical/rehabilitation period is defined in Section [5.4.3](#). Total rFIXFc consumption will be determined as the sum of all doses administered during the referenced time periods.

	Statistical Analysis Plan	Final v1.0
---	----------------------------------	-------------------

#### **7.5.3.5. Summary of Bleeds per Major Surgery**

The total number of bleeding episodes per major surgery during the surgical/rehabilitation period will be summarized categorically (0, 1, 2, 3, >3) and with descriptive statistics. The total number of surgeries with a bleeding episode with onset during Days 1 to 3, Days 4 to 7, Days 8 to 14, and Days 15 to 28 during the surgical/rehabilitation period will be summarized categorically for all major surgeries for the FAS. A surgery will be included in each interval of time for which there was a bleeding episode that started during that time interval. If a bleeding episode started and resolved and another bleeding episode then started within a given time interval, that surgery will be counted only once in that interval. A bleeding episode that starts in one time interval and continues into the next one will be counted only in the interval in which it started. Percentages for this summary will be based on the number of patients still in the surgical/rehabilitation period during the respective interval of time.

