Phase 3 study 9HB01EXT is an ongoing open-label, multicenter extension study of the long-term safety and efficacy of rFIXFc in PTPs who completed other studies such as Study 998HB102 and 9HB02PED. As of 17 October 2014, the type and incidence of AEs observed in the study were generally similar to what is expected for the general adult and pediatric hemophilia population. The results from this study as of that date suggested that, in line with the parent studies (Studies 998HB102 and 9HB02PED), rFIXFc treatment during the extension study was well tolerated and effective for the prevention and treatment of bleeding and for routine prophylaxis using either a weekly regimen, an individualized regimen with injections approximately every 2 weeks, or a personalized regimen. Surgical data from 15 major surgeries in 8 subjects confirmed the efficacy of rFIXFc for perioperative management in major surgery.

For further details regarding the clinical studies conducted with rFIXFc, and for descriptions of the potential risks and benefits of rFIXFc, refer to the rFIXFc Investigator's Brochure.

CONFIDENTIAL

The information contained herein may not be used, disclosed, or published without the written consent of Bioverativ
Therapeutics Inc

Table 1: Comparison of rFIXFc PK Parameters by Age Category: Geometric Mean (95% Confidence Interval [CI])

Summary of FIX PK parameters by age category: geometric mean (95% CI) - noncompartmental methods - one-stage clotting assay
 Pharmacokinetic Analysis Set

PK parameter	Pediatric study (9HB02PED)		Phase 3 study (998HB102)	
	<6 years (n=11)	6 to <12 years (n=13)	12 to 17 years (n=11)	>=18 years (n=109)
DNAUC (IU*h/dL per IU/kg)	22.71 (20.32, 25.38)	28.53 (24.47, 33.27)	29.50 (25.13, 34.63)	32.44 (30.95, 34.00)
t _{1/2} (h)	66.49 (55.86, 79.14)	70.34 (60.95, 81.17)	82.22 (72.30, 93.50)	76.36 (73.04, 79.83)
CL (mL/h/kg)	4.365 (3.901, 4.885)	3.505 (3.006, 4.087)	3.390 (2.888, 3.979)	3.083 (2.941, 3.231)
MRT (h)	83.65 (71.76, 97.51)	82.46 (72.65, 93.60)	93.46 (81.77, 106.81)	88.30 (84.72, 92.03)
V _{ss} (mL/kg)	365.1 (316.2, 421.6)	289.0 (236.7, 352.9)	316.8 (267.4, 375.5)	272.2 (258.3, 286.8)
IR (IU/dL per IU/kg)	0.590 (0.515, 0.675)	0.717 (0.612, 0.841)	0.847 (0.677, 1.060)	0.964 (0.907, 1.025)

Note 1: For the purpose of this table, all treatment arms in the Phase 3 study have been grouped together.

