  - If all of the dates mentioned above are missing, then the select the date of the end of surgery and impute 23:59 for the time. If the end date of the surgery is missing, then select the start date of the surgery and impute 23:59 for the time.
- If the overall end of study is declared while the patient is still in the surgical/ rehabilitation period then select the date of the end-of-study visit and impute 23:59 for the time if a time is not provided.

Two exceptions are noted:

- If 2 (or more) major surgeries are performed without an intervening discharge from the hospital, then the first surgical/rehabilitation period will end 1 minute before the start of the next surgery and the second surgical/rehabilitation will end as described above. The same will also apply among overlapping minor surgeries.
- If minor surgery is performed during postoperative care or rehabilitation then the surgical/rehabilitation period for the minor surgery will start and end on the day of the minor surgery, at 00:01 and 23:59, respectively, if times are not otherwise provided or

	Statistical Analysis Plan	Final v1.0
---	----------------------------------	-------------------

recorded as 00:00. The surgical/rehabilitation period for the major surgery will include the minor surgery (i.e., the surgical/rehabilitation period for the major surgery does not stop and restart around the minor surgery) and will end as otherwise defined.

The surgical/rehabilitation period will be determined in the same manner for both major and minor surgeries.

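### The interval table of bleeds after major surgery divides a count of surgeries by a count of patients, which inflates the percentage in any interval where there is a bleed and one patient has two or more surgeries at risk.

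*SAP*

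**What the plan says.** SAP section 7.5.3.5 has two parts. The first summarizes the number of bleeds per major surgery over the surgical/rehabilitation period. The second splits the post-operative time into Days 1 to 3, 4 to 7, 8 to 14 and 15 to 28, and this second part is at issue.

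- What is counted: "The total number of surgeries with a bleeding episode with onset during Days 1 to 3", and likewise for the later intervals.
- How it is counted: "A surgery will be included in each interval of time for which there was a bleeding episode that started during that time interval". A surgery counts at most once per interval.
- What it is divided by: "Percentages for this summary will be based on the number of patients still in the surgical/rehabilitation period during the respective interval of time".

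The neighbouring surgery summaries use a different unit in the denominator:

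- Section 7.5.3.1, surgeon's response: "Percentages will be based on the number of surgeries for which a response was provided".
- Section 7.5.3.2, injections: "Percentages for the categorical summary will be based on the number of major surgeries".
- Section 7.5.3.3, transfusions: "Percentages in the categorical summaries will be based on the number of major surgeries for which the respective data is available".

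Section 5.4.3 provides for repeat surgery with a rule that begins "If 2 (or more) major surgeries are performed without an intervening discharge from the hospital". Nothing in the SAP says that patients, in the denominator of 7.5.3.5, means patient-surgeries. Section 10, on changes from the protocol, does not mention the point.

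**The concern.** A percentage whose numerator counts operations and whose denominator counts people is neither a proportion of operations nor a proportion of people. The intervals are days after an operation. A boy with two major operations months apart can therefore add two surgeries to the Days 1 to 3 numerator and still count as one patient in the denominator.

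The table has a purpose of its own. Section 5.4.2.1 takes surgical/rehabilitation periods out of the efficacy period, so bleeds in those periods do not enter the annualized bleeding rate. Section 7.5.3.5 is where bleeds around major surgery are summarized, and it is the only planned summary by post-operative interval. With few operations, one patient with a repeat operation would shift the percentage visibly.

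**Working it through.** The documents give no figure for this table, so there is nothing to reproduce. The check compares three ratios for one interval.

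**Inputs.** The units come from the SAP sections quoted above. The counts of patients, surgeries and bleeds are assumptions, because the documents give no expected number of major or repeat surgeries in this trial. The one real ratio available is in protocol section 5.1.4, for the extension study: "Surgical data from 15 major surgeries in 8 subjects". Those were previously treated patients, so it serves only as an illustration.

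**Formulas.** Let B be the surgeries with a bleed starting in the interval, S the surgeries at risk (still in their surgical/rehabilitation period), P the distinct patients at risk, and Bp the patients with a bleed.

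- As written: B / P
- Per surgery: B / S
- Per patient: Bp / P
- As written relative to per surgery, when B > 0: (B / P) / (B / S) = S / P

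Each patient at risk has at least one surgery at risk, so S ≥ P. The figure as written is therefore never below the per-surgery figure. It is strictly above it only if B > 0 and S > P.

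**Assumed cases.**

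| At risk in the interval | B | As written | Per surgery | Per patient |
|---|---|---|---|---|
| 4 patients, 4 surgeries | 1 | 1/4 = 25% | 1/4 = 25% | 1/4 = 25% |
| 4 patients, 5 surgeries | 1 | 1/4 = 25% | 1/5 = 20% | 1/4 = 25% |
| 4 patients, 5 surgeries; both bleeds in the patient with two | 2 | 2/4 = 50% | 2/5 = 40% | 1/4 = 25% |
| 1 patient, 2 surgeries | 2 | 2/1 = 200% | 2/2 = 100% | 1/1 = 100% |
| 4 patients, 5 surgeries | 0 | 0% | 0% | 0% |
| 4 patients; a fifth surgery is no longer at risk | 1 | 1/4 = 25% | 1/4 = 25% | 1/4 = 25% |

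**All patterns for a small case.** Take 3 patients and 4 surgeries, with one patient having two. Each surgery is not at risk, at risk without a bleed, or at risk with a bleed. That gives 3^4 − 1 = 80 patterns with someone at risk.

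- Both surgeries of the repeat patient are at risk in 2 × 2 × 3 × 3 = 36 patterns.
- In 1 × 2 × 2 = 4 of these no surgery has a bleed.
- The figure as written is therefore too high in 36 − 4 = 32 patterns, equal to the per-surgery figure in 48, and lower in none.

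**Extension-study ratio, all surgeries assumed at risk.** S / P = 15 / 8 = 1.875. Three surgeries with a bleed would read 3/8 = 37.5% instead of 3/15 = 20.0%. Nine would read 9/8 = 112.5% instead of 9/15 = 60.0%.

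**The case against.** The strongest reply is that this is loose wording. Section 5.4.3 defines a surgical/rehabilitation period for each surgery, the section is titled per major surgery, and the neighbouring sections divide by surgeries. A programmer might well read patients still in the period as surgeries still at risk and build the right table. That is plausible and supports the proposed correction, but no passage says it. Followed literally, the rule gives the mismatched ratio.

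A second reply is that the excess depends on the reference. Against a per-patient percentage, the figure is too high only if one patient bleeds after two surgeries in the same interval. In the second row of the table above, 25% is a correct per-patient proportion. This is right, but the numerator counts surgeries, so the matching reference is per surgery. In the third row, 50% is wrong on either basis.

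Three stronger readings are tempting, and the documents do not support them.

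- A reader might infer that any repeat surgery inflates the table. It does not. There must be a bleed in the interval and two surgeries of one patient at risk in it. Where a second major operation follows without discharge, section 5.4.3 ends the first period one minute before it, so the first surgery can drop out of later intervals.
- A reader might take 1.875 as the expected or largest factor. It is neither. It comes from another population, while this trial enrols mainly very young children, and protocol section 10.2.7 classes port placement and removal as minor surgery. The true factor can be smaller or larger in each interval.
- A reader might infer that conclusions about surgical hemostasis are compromised. The surgeon's response at 24 hours is summarized separately with a surgery denominator. Bleeds in the first 14 days after major surgery are listed, and SAP section 12 also plans a general listing of injections and treated bleeds. The first part of 7.5.3.5 does not use this denominator.

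**Conclusion.** The denominator is wrong as written. In an interval with at least one bleed, where some patient has two or more major surgeries at risk, the percentage exceeds the per-surgery percentage by the factor S / P and can exceed 100%. In every other interval it is unchanged. If no patient has a repeat major operation, the two rules give the same table.

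The size in this trial cannot be predicted from the documents. One repeat operation among 4 patients at risk gives a factor of 5/4 = 1.25, on assumed counts. The importance is minor: the table is descriptive, it sits among the exploratory analyses, and no hypothesis is tested. The primary endpoint, inhibitor development, does not depend on it.

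**What to change.** In the last sentence of SAP section 7.5.3.5, replace the count of patients with the number of major surgeries whose surgical/rehabilitation period is still ongoing in that interval. This keeps the at-risk logic, matches the unit used in 7.5.3.1 to 7.5.3.3, and holds every percentage at or below 100%. Printing that number beside each percentage would also let a reader see how few surgeries it rests on.

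The cost is one phrase in the SAP and one line of programming. No new data are needed and no other analysis changes.

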## 8. PHARMACOKINETIC ANALYSIS

Pharmacokinetic samples are collected during the course of this study at baseline and interim visits. Additionally for patients undergoing ITI, PK samples are collected for the determination of incremental recovery (IR) after a confirmed negative inhibitor in patients undergoing ITI (further details are in Section 7.4.9).

PK activity data will be listed for the main study population and separately for measurements taken during the ITI period.

Activity measurements of the form “<x” (i.e., below the lower limit of quantification [LLOQ]) or “>x” (i.e., above the upper limit of quantification [ULOQ]) will be imputed as “x” in the calculation of PK parameters but displayed as “<x” or “>x” in the listings.

IR is calculated using the following formula:

$$\text{IR (IU/dL per IU/kg)} = \frac{(\text{C}_{\text{max}} \text{ for FIX activity} - \text{Pre-dose FIX activity})}{\text{Actual dose (IU/kg)}} \quad (\text{IU/dL})$$

where:

- $C_{\text{max}}$  (maximum concentration) is 30-minute FIX activity post-dose
- FIX activity <0.5 IU/dL was set to 0 IU/dL for calculation of IR.

IR data will be listed and summarized by visit in the FAS for exposure on the episodic and prophylactic treatment regimens.

### Repeat Analysis Acceptance Criteria

If the assay value is considered as incongruous or aberrant result, the following calculations and comparisons should be used to accept the repeated result and select the reported value:

- For the repeat analysis to be acceptable, the difference between the original and repeat values should be <40% as calculated below:

$$[(\text{Original} - \text{Repeat})/\text{mean}] \times 100 < 40\%$$

If this condition is not met, reject the reanalysis and perform repeat analysis in duplicate or report “no result” (NR, e.g., in case of insufficient sample volume).

- If the repeat values are acceptable, the selected value to report will be the mean of the original value and the repeat value.

	Statistical Analysis Plan	Final v1.0
---	----------------------------------	-------------------

## 9. SAFETY ANALYSIS

### 9.1. General Safety Principles

Safety analyses will be based on the Safety Analysis Set and unless otherwise specified, presented by the treatment regimen groups described in Section 5.1.1.

### 9.2. Analysis of Primary Endpoint or specified safety endpoints

The primary safety endpoint is the occurrence of inhibitor development as determined from the Nijmegen-modified Bethesda assay. Analysis of the incidence of positive inhibitor formation is detailed in Section 9.4.3.

### 9.3. Adverse Events

An adverse event (AE) is any untoward medical occurrence in a patient or clinical investigation subject administered a pharmaceutical product that does not necessarily have a causal relationship with this treatment. An AE can therefore be any unfavorable and unintended sign (including an abnormal laboratory finding), symptom, or disease temporally associated with the use of a medicinal (investigational) product, whether or not related to the medicinal (investigational) product.

Bleeding episodes in this patient population are not considered as AEs. Bleeding episodes that meet a serious criterion should be reported as serious adverse events (SAE).

AEs will be classified using the Medical Dictionary for Regulatory Activities (MedDRA) system organ classes and preferred terms. MedDRA version 21.1 will be used in this study. All AEs will be listed.

The incidence of AEs will be summarized by system organ class (SOC) and preferred term (PT). Summaries will be included for all AEs as well as by severity and relationship to treatment. Patient listings will be provided for all AEs, SAEs, related AEs, AEs resulting in discontinuation of study treatment and/or withdrawal from the study, AEs during major surgical/rehabilitation periods, and deaths.

AEs that occurred during major surgical/rehabilitation periods will be included in the overall (top-line) summary of AEs but not in any of the other AE tables. Consideration is given to adverse events with an onset date at the start of the surgical/rehabilitation period in the event the pre-surgical dose was administered the day before the surgery.

All AE listings will include the onset and resolution study days relative to Study Day 1, which is the date of the first rFIXFc treatment. AEs that are emergent prior to the first rFIXFc treatment, AEs that are emergent during a major surgical/rehabilitation period, and AEs that are emergent on the day of surgery will be flagged. Similarly, AEs that are emergent after inhibitor development will be indicated separately as per the period during which they occurred.

Events of overdose will not be included in the AE summary tables unless they are determined to be AEs.

	Statistical Analysis Plan	Final v1.0
---	----------------------------------	-------------------

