16.5. Safety

Unless specified otherwise in the SAP, safety data will be summarized overall. Subjects developing a confirmed positive inhibitor test after exposure to rFIXFc study drug (the Inhibitor Subgroup) will have their safety data included up to the time of the last negative inhibitor test; safety data collected after the time of the last negative inhibitor test will be summarized separately.

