16.5.2.2. Adverse Events

AEs will be coded using the Medical Dictionary for Regulatory Activities. The incidence of AEs will be summarized by system organ class and preferred term. Summaries will be for all AEs as well as by severity and relationship to treatment. Subject listings will be provided for all AEs, SAEs, AEs resulting in discontinuation of study treatment and/or from the study, and deaths.

Unless otherwise specified in the study SAP, AEs and SAEs occurring during treatment with the ITI regimen will be summarized and listed separately. Serious pretreatment events will be included and identified in the SAE listing, but only serious events occurring after the start of treatment will be summarized.

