#### **5.4.3. Surgical/Rehabilitation Period**

The broadest span of time for the surgical/rehabilitation period is from the first dose of rFIXFc given for the surgery (i.e., the pre-surgery dose) up to 1 minute before the first regular prophylactic dose after the last day of postoperative care/rehabilitation. Since not all patients will have these events, specific considerations for the start and end of the surgical/rehabilitation period are as follows:

	Statistical Analysis Plan	Final v1.0
---	----------------------------------	-------------------

Start of the surgical/rehabilitation period:

- If there is more than one pre-surgical dose then the first one should be selected (a pre-surgical dose can be administered the day before the surgery).
- If there is no pre-surgical dose but there is a prophylaxis dose or dose given for “OTHER” reason prior to the surgery on the day of or the day before surgery, the last of these doses should be selected.
- If there is no pre-surgical dose or a prophylactic dose the day before surgery then select the start date/time of the surgery. If the time was not recorded then select the date and impute 00:01 for the time.

End of the surgical/rehabilitation period:

- 1 minute before the first regular prophylactic dose on or after the last date among the dates for discharge from the hospital, post-operative visit 1, post-operative visit 2, and the end of rehabilitation.
- If all of the dates mentioned above are missing, then select the first prophylactic dose after the date/time for the end of surgery. If the surgery time was not recorded then select the surgery date and impute 23:59 for the time. If the end date of the surgery is missing then select the start date of the surgery and impute 23:59 for the time.
- If the patient is not on prophylactic regimen following the surgical/rehabilitation period (e.g., the patient is on episodic regimen after completing the surgical/rehabilitation period, or the patient simply received no further prophylactic doses), then the end of the surgical/ rehabilitation period is:
  - Imputed as 23:59 on the last date among the dates for discharge from the hospital, post-operative visit 1, post-operative visit 2, and the end of rehabilitation.

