#### **9.3.7. Serious Adverse Events**

Any AE reported as resulting in death, immediate risk of death (life threatening), inpatient hospitalization or prolongation of existing hospitalization, persistent or significant disability/incapacity, or a congenital/anomaly/birth defect will be classified as an SAE. An SAE may also be any other medically important event that, in the opinion of the Investigator, may jeopardize the patient or may require intervention to prevent one of the other outcomes listed above. Events considered medically important, as defined in Section 15.3.2 of the protocol, are also considered to be SAEs.

All SAEs will be listed; treatment-emergent SAEs will be summarized overall by SOC and preferred term.

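### AEs arising in major surgical/rehabilitation periods are kept out of every AE table except the top-line one, although the protocol plans the breakdowns for all AEs

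*SAP*

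**What the plan says.** Protocol Section 16.5.2.2 commits to a breakdown: "The incidence of AEs will be summarized by system organ class and preferred term". It then sets the scope: "Summaries will be for all AEs as well as by severity and relationship to treatment". It names two special groups. For immune tolerance induction (ITI), "AEs and SAEs occurring during treatment with the ITI regimen will be summarized and listed separately", unless the SAP specifies otherwise. Serious pretreatment events go into the listing, but "only serious events occurring after the start of treatment will be summarized". Surgery is not mentioned.

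SAP Section 9.3 repeats that AE summaries cover all AEs, with splits by severity and relationship. Two sentences later it says that AEs in major surgical/rehabilitation periods "will be included in the overall (top-line) summary of AEs but not in any of the other AE tables". The sections defining the detailed tables do not repeat the exclusion. Section 9.3.7, for example, says "treatment-emergent SAEs will be summarized overall by SOC and preferred term".

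SAP Section 5.4.3 defines the window. It opens with the pre-surgery dose and, for a patient who returns to prophylaxis, ends "1 minute before the first regular prophylactic dose on or after the last date among the dates for discharge from the hospital", the post-operative visits and the end of rehabilitation. No maximum length is given.

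**The concern.** Safety is the primary objective, and the detailed AE tables show which events occurred, how severe they were and whether they were judged related. Under the SAP rule, an AE that starts between the pre-surgery dose and the return to regular prophylaxis after major surgery appears in none of them.

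Protocol Section 15.3.2 makes four kinds of event mandatory SAEs: a confirmed inhibitor, an allergic reaction of Grade 2 or greater, a vascular thrombotic event (other than injection-site thrombophlebitis) and major surgery itself. With onset in the window, none of these would have a SOC/PT, severity or relationship row.

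Two consequences follow: detailed incidences that err in one direction only, and a top-line SAE count that the SAE table does not support.

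**Working it through.** There is no stated figure to reproduce. The check is a comparison of texts plus one line of arithmetic.

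**Step 1. How the documents treat data that they set apart.**

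| Data set apart | Where | Still summarized? |
|---|---|---|
| AEs during ITI | Protocol 16.5.2.2 | Yes, separately |
| Safety data after the last negative inhibitor test | Protocol 16.5 | Yes, separately |
| Serious pretreatment events | Protocol 16.5.2.2 | No, listing only, as the protocol states |
| AEs in major surgical/rehabilitation periods | SAP 9.3 only | Top-line counts only |

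The protocol gives no basis for the last row. Its Section 16.2.2 introduces the surgical/rehabilitation period to select data for efficacy analyses, not safety.

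**Step 2. Which outputs carry these events.** From SAP Sections 9.3 to 9.3.8 and the index in Section 12:

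- Included: the top-line summary (any treatment-emergent AE, related AE, SAE, related SAE, discontinuation, death), the AE listings with a flag, and a dedicated surgical-period listing.
- Excluded: the tables by SOC/PT, descending incidence, severity, relationship, SAE and discontinuation.
- No replacement: the index has no surgical-period AE table. The surgery tables in SAP 7.5.3 cover haemostatic response, injections and dose, blood loss and transfusions, consumption and bleeds.

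**Step 3. Direction of the error.** SAP 5.1.1.2 gives the Safety Analysis Set as the denominator for AE percentages. Patients who have major surgery remain in it while their surgical-period events leave the numerator. A detailed row can stay the same or fall; it cannot rise.

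**Step 4. Reconciliation.** Protocol 10.2.7 and 15.3.2 make every major surgery an SAE. Protocol 10.2.7 allows major surgery on study only after at least 3 exposure days, so the event is treatment-emergent. The operation lies inside the window by construction. Each such SAE is in the top-line row and absent from the SAE table. The two patient counts differ by the number of patients who have no other SAE outside the window.

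**Step 5. Weight of one patient.** Under SAP 9.3.3 a patient counts once per term. Let N be the number of treated patients and m the number whose only occurrence of the term falls in the window. The row falls by 100 × m/N percentage points.

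- N = 30 (SAP 3.3, approximate), m = 1: 100/30 = 3.3 points.
- N = 20 (taken as a low case), m = 1: 100/20 = 5.0 points.
- A patient who also has the term outside the window contributes m = 0, and that incidence row does not change.

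The documents give neither m nor an expected number of major surgeries.

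**The case against.** The best defence is Protocol Section 16.5: "Unless specified otherwise in the SAP, safety data will be summarized overall". That gives the SAP latitude, and the exclusion is written down in advance. It is also a consistent design choice, since SAP 9.4 and 9.5 keep laboratory values and vital signs from major surgical periods out of summaries. SAP 10 claims to list only major differences. The rule is narrow too: Protocol 10.2.7 classes port placement or removal, minor dental extractions and simple excisions as minor surgery, so AEs around them stay in every table.

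Most of this stands as a limit on size, but it does not remove the conflict. The Section 16.5 clause concerns overall versus split presentation. It does not clearly allow events to be left out of the breakdowns altogether, and the other post-treatment periods that the protocol separates are still summarized. If the sponsor relies on the clause, SAP 10 is still the place to say so.

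A reader might infer more than the documents support:

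- That related or serious surgical-period events appear in no incidence table. They do: SAP 9.3.2 gives numbers and percentages for both in the top-line table. What is missing is the breakdown.
- That the primary endpoint is affected. SAP 9.4.3.1 includes inhibitor samples taken during surgical/rehabilitation periods. An inhibitor SAE with onset in the window would be missing only from the detailed AE tables.
- That every excluded event moves its row by 3.3 points. That holds only for a patient with no other occurrence of the term.
- That follow-up time is removed. No rule removes it, and the events remain in the top-line counts.

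**Conclusion.** The conflict is real and should be corrected. SAP 9.3 contradicts Protocol 16.5.2.2 and its own statement that summaries cover all AEs, and SAP 10 does not declare the change. Detailed AE incidences can only be understated, and the top-line SAE count and the SAE table will not reconcile once a major surgery occurs, at event level in every case and at patient level where that patient has no other SAE.

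The size is 3.3 percentage points per row for each patient whose only occurrence of the term falls in the window, assuming about 30 treated patients. The total effect depends on the number of major surgeries, which is not stated and may be small; with none, it is nil. The reconciliation point assumes that the surgery SAE is recorded with onset at the operation. This is a fault in tabulation and documentation, not a loss of data.

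**What to change.** Preferred: include AEs from major surgical/rehabilitation periods in all treatment-emergent tables, with a footnote identifying them or a supplementary version that leaves them out.

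The column must be settled at the same time. SAP 5.3.4 adds up the prophylactic durations before and after surgery, so a surgical-period AE has no defined regimen column. Count it in the overall column, which SAP 5.1.1 already provides for safety data, and assign it to the regimen in effect before surgery. The same rule should govern the top-line table.

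Alternative: keep the exclusion and add a surgical-period summary by SOC/PT, severity, relationship and seriousness.

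Either way, record the choice in SAP 10 and keep the planned surgical-period listing.

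The cost is SAP wording, a change to one exclusion flag and a regimen-assignment rule. The downside of the first option is that procedure-related AEs appear in the main tables; the second needs one extra set of tables.
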